5.2 Exclusion Criteria

Current Condition or Medical History

1. History of life-threatening COPD including Intensive Care Unit admission and/or requiring intubation.
2. Hospitalizations for COPD, pneumonia, or Corona Virus Disease 2019 (COVID-19) in the 12 weeks prior to Screening and/or a positive COVID-19 test result indicating an active infection at Screening. Patients with COVID-19 antibodies from a previous exposure with no active infection are not excluded.
3. COPD exacerbation requiring oral or parenteral steroids within 3 months of Screening.
4. Previous lung resection or lung reduction surgery within 1-year of Screening.
5. Long term oxygen use defined as oxygen therapy prescribed for greater than 12 hours per day. As needed oxygen use (≤12 hours per day) is not exclusionary.

6. Pulmonary rehabilitation, unless such treatment has been in a stable maintenance phase for 4 weeks prior to Visit 1 and remains stable during the study.
7. Lower respiratory tract infection within 6 weeks of Screening.
8. Other respiratory disorders including, but not limited to, a current diagnosis of asthma, active tuberculosis, lung cancer, sarcoidosis, lung fibrosis, interstitial lung diseases, unstable sleep apnea, known alpha-1 antitrypsin deficiency, core pulmonale, clinically significant pulmonary hypertension, clinically significant bronchiectasis, or other active pulmonary diseases.
9. Major surgery (requiring general anesthesia) in the 6 weeks prior to Screening, lack of full recovery from surgery at Screening, or planned surgery through the end of the study.
10. Historical or current evidence of clinically significant cardiovascular disease defined as any disease that in the opinion of the Investigator would put the safety of the patient at risk through participation or which could affect the efficacy or safety analysis if the disease/condition were to exacerbate during the study, including, but not limited to:
 - Myocardial infarction or unstable angina within 6 months prior to Screening.
 - Unstable or life-threatening cardiac arrhythmia requiring intervention within 3 months prior to Screening.
 - Diagnosis of New York Heart Association (Dolgin 1994) Class III and Class IV heart failure.

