8.1.3 Medical/Surgical/ COPD/ and Smoking History

A history of relevant current or past medical conditions, surgical history, COPD history, and smoking history (current or former [yes or no]) will be obtained.

- Minor surgical procedures (eg, tonsillectomy, appendectomy) performed more than 5 years prior to Screening Visit 0 do not need to be recorded.
- COPD history will include COPD exacerbation history and COPD type (emphysema and/or chronic bronchitis), as assessed by the investigator or medical professional). Chronic bronchitis is defined as “regular production of sputum for three or more months in two consecutive years (in the absence of other conditions that may explain it [GOLD, 2020]).”
- Former smokers are defined as those who have stopped smoking for at least 6 months prior to Screening Visit 0.

Medical and COPD condition(s) identified during the Screening Visit will be documented as medical history and not as an AE(s) unless the condition worsens during the study and meets the definition of an AE.

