The proportion of responders on the SGRQ, patients with an improvement of at least 4 units, will be compared between treatment groups using a logistic regression model with fixed factors treatment, region, and background medication strata, and smoking status. Imputation of missing data will be done similar as for continuous endpoints. A sensitivity analysis will be performed in which patients with missing data at the required visit will be considered a non-responder in the analysis.

The time to first COPD exacerbation during the 24 or 48 week treatment period, depending on stratification, will be visualized using a Kaplan-Meier plot and compared between treatment groups using the log-rank test, stratified by region, background

medication strata, and smoking status. As a secondary evaluation a Cox's proportional hazards model will be used with the same factors. Patients without exacerbations will be censored at last day in the treatment period, including period of recording after possible treatment withdrawal. The treatment difference in the Cox model will be expressed as a hazard ratio. Assumption of proportional hazards will be checked. The number of COPD exacerbations during the 24- or 48-week treatment period will be compared between treatments using a negative binomial model adjusting for treatment, region, background medication strata and smoking status and further using the log exposure time as an offset. The treatment difference from the negative binomial model will be expressed as an annualized risk ratio.

Subgroup analyses will be performed for the primary endpoint and selected secondary endpoints by gender, age-class (below or above 65 years), region, background medication strata, smoking status, ICS use, known chronic bronchitis, and FEV₁ reversibility at baseline ($\geq 12\%$ and ≥ 200 mL).

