10.1. DERIVATIONS

- BMI (kg/ m²) = weight (kg)/ height (m)²
- Time since initial diagnosis of COPD = (date of consent – date first diagnosed)/365.25
- Pack Years = Number of packs per day x number of years smoking

Reversibility status is calculated based on pre-bronchodilator and post-bronchodilator FEV₁ values taken at Screening. If patient has increase of $\geq 12\%$ and $\geq 200\text{mL}$ then patient is reversible, else patient is non-reversible.

Age (years) collected in the eCRF will be used for the analysis.

Pack Years is automatically calculated in the eCRF and this value will be used in the summaries. COPD severity will be derived as follows based on post-bronchodilator screening spirometry:

- Mild: post-bronchodilator FEV₁ $\geq 80\%$ predicted
- Moderate: $50\% \leq$ post-bronchodilator FEV₁ $< 80\%$ predicted
- Severe: $30\% \leq$ post-bronchodilator FEV₁ $< 50\%$ predicted
- Very severe: post-bronchodilator FEV₁ $< 30\%$ predicted
-

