16.3.3. ANALYSIS OF OTHER EFFICACY VARIABLES

Change from baseline to average FEV₁ AUC_{6-12h} will be analyzed using ANCOVA approach and missing data will be imputed using imputation, as described in Sections 16.1.3 and 16.2.2.1 of

[REDACTED]

the SAP, respectively.

Model assumptions will be tested and solved, if failed, as per Section 16.1.3 of the SAP.

The rate of and time to first moderate/severe COPD exacerbations will be analyzed in three cut-off rules:

- All patients (patients in 24-week and 48-week strata combined) using full study length
- Period truncated at Week 24 visit (patients in 24-week and 48-week strata combined)
- Patients in 48-week stratum using full study length

For each of the three rules above, the number of patients who experienced COPD exacerbation will be presented by week, follow-up and overall. Similarly, the duration of COPD exacerbation (in days) and the time in study will be calculated based on the cut-off rules.

Weekly percentage of patients who experienced COPD exacerbation will be based on the treatment population being analyzed. For All patients and Period truncated at Week 24 visit, the percentage will have denominator of mITT population. Analysis using 48-week stratum only will have mITT patients in this stratum as denominator.

For each cut-off rule, the number of moderate/severe COPD exacerbations will be analyzed using a negative binomial model adjusting for treatment, region, actual background medication strata and actual smoking strata, as well as using log study time (years) as an offset. If the model does not converge, the covariate that causes the issue will be removed from the model. The number of patients who experienced exacerbations and the number of exacerbations will also be presented using the data used to analyze negative binomial model.

The logic for time in study used as offset or for censoring purpose is as follows:

- For 24-week completers, use the day of final week 24 clinic visit. For 48-week completers, use the day of the final week 48 clinic visit.
- For non-completers who are not lost to follow-up, use the end of study date, which is assumed to be their end of study visit.
 - If no end of study date, use the last site contact out of any assessment (excluding eDiary)
- For subjects who are lost to follow-up, the censoring date will be at their last reported site contact.

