Moderate/severe exacerbations occurring after the day used as offset will not be considered in the analysis. The treatment difference from the negative binomial model will be expressed as an

[REDACTED]

annualized risk ratio. The data will also be summarized by treatment group over duration of the study period. Only moderate/severe COPD exacerbations meeting the protocol-specified criteria will be presented in the listing.

Time to study medication withdrawal or study withdrawal will be presented per stratum and by the following subgroups: patients who withdrew from study medication/study before Week 24 visit and patients who withdrew from study medication/study before Week 48 visit for 48-week stratum.

Time to first moderate/severe COPD exacerbation during the study period will be presented for all patients using full study length, all patients using data truncated at week 24 visit, and patients in 48-week stratum. The primary analysis will include log-rank test stratified by region, actual background medication strata and actual smoking strata. Summary of number of patients with events and number of patients censored will be presented. Outcome will be visualized using a Kaplan-Meier plot.

The health index and VAS score for EQ-5D-5L questionnaire will be analyzed using ANCOVA approach, as described in Section 16.1.3 of the SAP, with data imputation described in Section 16.2.2.3 of the SAP.

HRU over a period truncated up to Week 24 visit for all patients (24-week and 48-week strata combined) and for 48-week stratum only will be summarized for each event and for overall count. HRU during follow-up period will not be presented.

- Sensitivity analysis or subgroup analysis may be considered following results of the patient perception survey. The survey will be summarized to investigate if there are any signs of breaching of the blind related to the appearance of study medication.
- Proportion of E-RS total score responders will be analyzed by means of a logistic regression model with fixed effects for treatment, region, actual background medication strata and actual smoking strata at baseline and baseline E-RS total score as covariate. Missing data will be imputed as described in Section 16.2.2.3 (range method).

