16.3.4. SENSITIVITY ANALYSIS OF OTHER EFFICACY VARIABLES

Sensitivity analysis with no data imputation, including only patients with data collected at the required visit while still on randomized treatment at scheduled visit, or at end of study visit within the visit window will be performed on the health index and VAS score for EQ-5D-5L questionnaire and analyzed using ANCOVA approach, as described in Section 16.1.3 of the SAP.

For E-RS total score responder analysis a sensitivity analysis using other approaches MI imputation using the continuous data method described in Section 16.2.2.1.

Sensitivity analysis for time to first moderate/severe COPD exacerbation will be done for the three data groups used in the main analysis: all patients, period truncated at week 24 visit, and patients in 48-week stratum, as described in Section 16.3.3 of the SAP. The analysis will be done using Cox proportional hazards regression model stratified by region, background medication strata and smoking strata. Patients without exacerbations will be censored (as described in the logic for time in study above) at last day in the treatment period, including period of recording after possible treatment withdrawal. Moderate/severe COPD exacerbations that happened in the follow-up period will be excluded from the analysis since these occur after censoring. The treatment difference in the Cox model will be expressed as a hazard ratio.

Testing proportional hazard assumptions:

1. Check that the covariates are independent of each other through proc phreg in SAS software.
2. Check that the hazard (hazard ratio) is independent of time through log(-log(survival)) vs log(time) plot and an interaction test for treatment times log(time).

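### The exacerbation rate model and the sensitivity Cox model omit exacerbation history and screening FEV1, forgoing a small gain in precision for the rate ratio

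*SAP*

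**What the plan says.** **Rate model.** Protocol 9.4.1 plans a "negative binomial model adjusting for treatment, region, background medication strata and smoking status and further using the log exposure time as an offset". SAP 16.3.3 keeps those terms: the count "will be analyzed using a negative binomial model adjusting for treatment, region, actual background medication strata and actual smoking strata". If the fit fails, the SAP removes whichever covariate is responsible.

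**Time to first exacerbation.** SAP 16.3.3 states: "The primary analysis will include log-rank test stratified by region, actual background medication strata and actual smoking strata". The sensitivity analysis in SAP 16.3.4 is a "Cox proportional hazards regression model stratified by region, background medication strata and smoking strata".

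**What is available before randomization.** Protocol 8.1.3 states that "COPD history will include COPD exacerbation history and COPD type". For lung function, SAP 10.1 states that "COPD severity will be derived as follows based on post-bronchodilator screening spirometry". The SAP uses severity for disposition, the baseline table and subgroups (7.5, 10), but in no exacerbation model. Exacerbation history does not appear in the baseline list of SAP 10.

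**What the SAP does elsewhere.** The ANCOVA models include baseline (16.1.3, 16.2.3.1), with BDI serving as the baseline for TDI. The responder models for SGRQ, E-RS and morning trough FEV1 include the matching baseline value (16.2.3.2, 16.3.3). For SGRQ responders the protocol listed no baseline term and the SAP added one. SAP 7.1 names baseline as a general covariate but refers to each analysis section for its use, and the exacerbation section does not include it.

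**The concern.** Past exacerbations are the natural baseline counterpart of an exacerbation count, and FEV1 % predicted is a plausible second predictor. When predictors of the rate are left out of a negative binomial model, the differences they would explain go into the dispersion parameter and widen the interval for the rate ratio. The SAP avoids this for its other modelled endpoints and gives no reason for treating exacerbations differently.

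The effect on exacerbations is a stated objective (Protocol 3.1.3, SAP 2.3) and has no power calculation, so efficiency from data already collected is worth having. Because exacerbation history is not tabulated, a reader of the results also could not see whether the arms were alike on it. That gap does not depend on any assumed rate.

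**Working it through.** **The plan's own figure.** The only power statement is for FEV1 AUC0-12h (Protocol 9.2): 500 vs 300 patients, SD 250 mL, difference 59 mL, two-sided 5%, power 90%. Recalculation gives 89.8%, and a detectable difference of (1.960 + 1.282) x 250 x sqrt(1/300 + 1/500) = 59.2 mL. The figure reproduces, but it does not bear on exacerbations.

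**Inputs from the documents.** About 400 patients in each duration subset, allocated 1:1 (24 weeks) and 3:1 (48 weeks) under Protocol 4.1. That gives 200 + 300 on ensifentrine and 200 + 100 on placebo.

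**Assumed inputs (none is in the documents).**
- Placebo rate 0.2-0.8 per year; treatment rate ratio 0.7; no dropout.
- Residual dispersion k of 0.3-1.0.
- Exacerbation history in 25-40% of patients, with rate ratio 1.5-2.5.
- Severe disease in 40%, with rate ratio 1.2-1.6.

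**Formulas.** Let m be a patient's covariate multiplier scaled to mean 1, with variance CV². Leaving the covariates out raises the dispersion to (1 + k)(1 + CV²) - 1. The variance of the log rate ratio is the sum over arms of 1/I, where I is the sum over patients of mu/(1 + k mu), and mu is rate x years x multiplier.

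**Worked case:** rate 0.5, k = 0.3, history in 25% (rate ratio 2.0), severe disease in 40% (rate ratio 1.5).
- Mean multiplier: 1.25 x 1.20 = 1.50. Mean square: 1.75 x 1.50 = 2.625. CV² = 2.625/2.25 - 1 = 0.167.
- Unadjusted dispersion: 1.3 x 1.167 - 1 = 0.52.
- Unadjusted: I = 78.5 (placebo) and 112.9 (ensifentrine). Variance 0.01274 + 0.00886 = 0.02160; SE 0.1470.
- Adjusted: I = 82.6 and 117.8. Variance 0.01211 + 0.00849 = 0.02059; SE 0.1435.
- SE falls by 2.4% and variance by 4.6%. Power goes from 68.0% to 70.0%.

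**Across the grid (rate model).**

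| Case | SE of log rate ratio | Change in SE | Power |
|---|---|---|---|
| Rate 0.2, k 1.0, weak predictors | 0.2298 to 0.2292 | -0.3% | 34.2% to 34.3% |
| Rate 0.5, k 0.3, middle | 0.1470 to 0.1435 | -2.4% | 68.0% to 70.0% |
| Rate 0.8, k 0.3, strong | 0.1243 to 0.1174 | -5.6% | 81.9% to 86.0% |
| Rate 0.8, k 1.0, strong | 0.1430 to 0.1355 | -5.3% | 70.3% to 75.0% |

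Overall, SE falls by 0.3-5.6%, variance falls by 0.6-10.8%, and power rises by 0.1-4.7 points.

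**Simulation (250-400 trials per scenario, k = 0.5), without and with the two covariates.**

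| Scenario | Rate-model SE | Cox SE | Cox log hazard ratio | Cox power |
|---|---|---|---|---|
| Rate 0.3, rate ratio 0.6, middle | 0.1963 to 0.1939 | 0.1998 to 0.2006 | -0.475 to -0.482 | 66.2% to 67.0% |
| Rate 0.5, rate ratio 0.7, weak | 0.1479 to 0.1471 | 0.1555 to 0.1559 | -0.321 to -0.323 | 56.1% to 56.6% |
| Rate 0.5, rate ratio 0.7, strong | 0.1546 to 0.1493 | 0.1580 to 0.1586 | -0.323 to -0.329 | 52.0% to 56.0% |

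The Cox SE does not fall. The estimate moves slightly away from zero because it is conditional on more covariates. The largest power gain, 4 points, comes from 250 trials, where one power estimate has a standard error of sqrt(0.52 x 0.48/250) = 3.2 points. In the low-rate scenario 30 of 400 trials were set aside because at least one of the two negative binomial fits gave no usable SE. This shows that convergence matters at low rates, but it does not isolate the added terms as the cause.

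**The case against.** The strongest reply is that the planned model is pre-specified, follows Protocol 9.4.1, and adjusts for region and two randomization strata. Randomization protects the comparison without further covariates. Exacerbations are an other endpoint, outside the seven-step hierarchy of SAP 7.4 and without a power claim. All of this stands, and it limits the point to efficiency.

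Several stronger readings are tempting, and the documents do not support them.

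- **That time-to-first-exacerbation results lose precision.** Covariates do not lower the Cox SE, as shown above. The main time-to-event analysis is the stratified log-rank test, which could use the covariates only as strata. It has 3 x 2 x 2 = 12 cells, and two more binary factors would make 48.
- **That the gain could reach about 20%.** At 0.6 per year over 24 weeks 1/mu is 3.61, so halving dispersion from 2 to 1 gives 5.61/4.61, or 22% more effective patients. If 30% of patients have a history, that halving needs a rate ratio for history of about 3.9; halving from 1 needs about 3. The documents offer no basis for effects that strong.
- **That patients must differ widely in underlying rate.** Entry does not require a history, but Protocol 5.2 excludes "COPD exacerbation requiring oral or parenteral steroids within 3 months of Screening", recent COPD hospitalization and life-threatening COPD. Protocol 5.3 excludes run-in exacerbations, and Protocol 5.1 limits post-bronchodilator FEV1 to 30-70% predicted. These narrow both predictors.
- **That the change costs nothing.** Protocol 8.1.3 gives no look-back, count format or grading for history, and the eCRF is not in the documents.
- **That the result is biased by imbalance.** With history in 30% and rate ratio 2, a chance difference at the 95% limit is 1.96 x sqrt(0.3 x 0.7 x (1/500 + 1/300)) = 6.6 points. That moves the rate ratio by about 0.066/1.3 = 5%. The test's error rate already allows for this.
- **That the pooled analysis with study 302 shares the gap.** It has its own SAP (SAP 1), which is not among these documents.

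**Conclusion.** The concern holds as a modest inefficiency. Two predictors obtained before randomization are left out of the negative binomial and Cox models, in contrast to the SAP's practice for its other modelled endpoints. If they are prognostic to the degree assumed, adding them makes the rate ratio more precise by a small amount, within the ranges above. For the hazard ratio the most to expect is a small power gain for a conditional effect.

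The size depends wholly on the assumed rates, dispersion and prognostic strength, and on full follow-up of 24 or 48 weeks. It would be smaller in the analysis truncated at Week 24, where each patient contributes fewer events and dispersion is a smaller share of the variance. The validity of the planned analyses is not in question.

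**What to change.** Before unblinding, amend the SAP as follows.

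1. In 16.3.3 and 16.3.4, add two covariates to the negative binomial and Cox models: screening post-bronchodilator FEV1 % predicted, and prior exacerbation history. Code history as the eCRF allows, state its look-back period, and give missing history its own category.
2. State the order in which covariates are dropped if a model does not converge, in place of the open rule in 16.3.3.
3. Add exacerbation history to the baseline characteristics in SAP 10.
4. Leave the stratified log-rank test unchanged.

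The cost is a few lines of SAP text, a check of how the eCRF records history, the related programming, and some added convergence risk if event rates are low. No new data collection is needed.

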16.3.4. SENSITIVITY ANALYSIS OF OTHER EFFICACY VARIABLES

Sensitivity analysis with no data imputation, including only patients with data collected at the required visit while still on randomized treatment at scheduled visit, or at end of study visit within the visit window will be performed on the health index and VAS score for EQ-5D-5L questionnaire and analyzed using ANCOVA approach, as described in Section 16.1.3 of the SAP.

For E-RS total score responder analysis a sensitivity analysis using other approaches MI imputation using the continuous data method described in Section 16.2.2.1.

Sensitivity analysis for time to first moderate/severe COPD exacerbation will be done for the three data groups used in the main analysis: all patients, period truncated at week 24 visit, and patients in 48-week stratum, as described in Section 16.3.3 of the SAP. The analysis will be done using Cox proportional hazards regression model stratified by region, background medication strata and smoking strata. Patients without exacerbations will be censored (as described in the logic for time in study above) at last day in the treatment period, including period of recording after possible treatment withdrawal. Moderate/severe COPD exacerbations that happened in the follow-up period will be excluded from the analysis since these occur after censoring. The treatment difference in the Cox model will be expressed as a hazard ratio.

Testing proportional hazard assumptions:

1. Check that the covariates are independent of each other through proc phreg in SAS software.
2. Check that the hazard (hazard ratio) is independent of time through log(-log(survival)) vs log(time) plot and an interaction test for treatment times log(time).

16.4. EVALUATION INCLUDING EXCLUDED SITES

Sites [REDACTED] were removed from the mITT. As a check of the impact of this exclusion the following analyses will be performed in the Extended mITT population.

[REDACTED]	[REDACTED]	[REDACTED]	[REDACTED]
[REDACTED]	[REDACTED]	[REDACTED]	[REDACTED]
[REDACTED]	[REDACTED]	[REDACTED]	[REDACTED]
[REDACTED]	[REDACTED]	[REDACTED]	[REDACTED]

- Analysis of FEV₁ AUC₀₋₁₂
- Analysis of peak FEV₁
- Analysis of E-RS total score
- Analysis of SGRQ total score
- Analysis of morning trough FEV₁
- Responder analysis of SGRQ total score

